### Secondary objectives:

### 1. Time to Event Endpoint

Multivariate Cox proportional hazards models will also be used to compare secondary outcomes including time to MACE, NACE, all-cause mortality, and treatment patterns (e.g., time to first fill, persistence) between study cohorts. (Additional model details will be provided in the SAP).

### 2. Resource Utilization, Costs, and Treatment Patterns

Cohort differences in continuous outcome variables will be analyzed using appropriate regression models based on the distribution of the study outcome. Medical costs will be modeled using generalized linear models (GLM) with a gamma specification and log link. Resource utilization outcomes (e.g., LOS, number of fills, ) will be modeled using ordinary least squares (OLS) regression. Counts of resource utilization and adherence (e.g., number of hospital admissions, PDC $\geq$ 80%) will be analyzed using logistic regression or negative binomial, depending on the frequency of events. Treatment cohort (prasugrel or clopidogrel), propensity score strata, and the cohort-by-propensity score strata interaction term will be included as independent variables in the models. Least squares means and 95% confidence intervals will be estimated on the difference in mean costs. Alternative and more appropriate models may be employed after assessment of the observed distribution of continuous dependent variables and prior to any outcomes analyses.

Multicolinearity and interaction between independent variables for all afore mentioned regression models will be examined and addressed as appropriate. A *p*-value <0.05 will be considered statistically significant with no adjustment for multiple comparisons. All analyses will be based on observed, not projected, data. All analyses will be conducted using SAS version 9.2 (SAS Institute, Inc., Cary, NC). The Benjamini-Hochberg method may be used

<sup>28 Benjamini, Y. and Hochberg, Y. (1995). Controlling the false discovery rate: A practical and powerful approach to multiple testing. *Journal of the Royal Statistical Society*, Series B, 57, 289-300.

as appropriate, particularly for analyses related to secondary objectives, to control for the multiplicity effect and mitigate the likelihood of obtaining any type 1 error.

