	Comorbidities/ Medical history	
 
Baseline comorbidities (n, %)
 
Arterial embolism, Asthma, Atrial fibrillation, Cardiac dysrhythmia, Cardiomyopathy, Cerebrovascular disease, Chronic Obstructive Pulmonary Disease (COPD), Deep venous thrombosis, Diabetes, Dyslipidemia, Dyspnea, Congestive Heart Failure (CHF), Hemorrhagic tendencies of blood dyscrasia, History of bleeding, Hypertension, Hypotension, Ischemic Heart Disease, other than ACS (MI or UA), TIA, Liver disease, Obesity, Osteoarthritis, Peripheral vascular disease, Phlebitis, Pulmonary embolism, Renal impairment (Renal failure, Chronic Kidney Disease (CKD), Other renal insufficiency), Rheumatoid Arthritis, Sepsis, Stroke (Hemorrhagic stroke, Ischemic stroke, Unspecified stroke), Thyrotoxicosis, thrombocytopenia, peptic ulcer disease (n, %)
 
Quan-Charlson Comorbidity Index (n, %, mean, SD, median)
 
0-1, 2, 3, 4+
 
	Y	Y
	Health care	All-cause medical encounters during baseline (n, %, mean, SD, median)	Y	N
		
 
Inpatient admissions
 
Length of inpatient stays
 
		

OBJECTIVE	VARIABLE	DEFINITION	CLAIMS	CHART
		
 
Outpatient visits (physician and outpatient hospital visits)
 
Other medical encounters
 
		
	Health care	All-cause costs during baseline (mean, SD, median)	Y	N
	resource costs	- Total (medical + pharmacy costs)	_	
		- Medical costs		
		- Inpatient costs		
		- Emergency department costs		
		- Outpatient costs		
		- Pharmacy costs		
	Health plan region	US Census geographic regions (n, %) - Northeast, Midwest, South, West	Y	Ν
	Index year	Year of the index hospitalization admission date	Y	Y
	Insurance type	Commercial, Medicare Advantage (n, %)	Y	N
	Primary payer type	HMO, PPO, POS, Other (n, %)	Y	N
	Prior MI	Yes, No (n, %)	Y	Y
	Prior	CABG, PCI (n. %)	Y	Y
	revascularization		_	
	Sex	Male, Female (n. %)	Y	Y
	Smoking status	Yes. No (n. %)	Ν	Y
	Socioeconomic	Race/ethnicity (n. %)	Y	Y
	status (SES)	- Caucasian, African American, Hispanic, Asian, Other		
	()	Income/Net worth (mean, SD, median)	Y	N
	Treatment	Baseline medication use (n. %)	Y	N
	utilization	- ADP-ri (clopidogrel, prasugrel, ticagrelor, ticlopidine).	_	
		phosphodiesterase inhibitor (cilostazol). HMG CoA		
		reductase inhibitors (statins), proton pump inhibitors.		
		antihypertensives (major class), antidiabetes medications		
		(major class)		
	Weight	Lbs/kg (mean, SD, median)	Y	Y

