## 9.6.2. Descriptive Analyses

Demographic, clinical, and other baseline variables (including resource use and cost) will be summarized by cohort and for overall group as the counts and percentages for categorical variables and means, median, standard deviation, min, and max for continuous variables. Differences between cohorts will be assessed using Chi-square test for categorical variables and t-test and ANOVA for continuous variables. Exact tests, bootstrapping and/or nonparametric tests will be used as appropriate. All tests will be two-sided.

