### Propensity score matching

Matching on propensity score can achieve a very high degree of balance between comparison groups and therefore, can mitigate confounding by baseline characteristics that may independently affect outcomes of interest. A propensity score for each subject will be defined as the probability of being in the prasugrel cohort and estimated using logistic regression. Prasugrel and clopidogrel subjects may be matched on their propensity scores using a greedy or optimal method to adjust for potential confounding bias.

The first step in the primary (propensity adjusted) analysis will be to estimate propensity scores for each patient using a forward step-wise logistic regression model with prasugrel cohort membership as the binary outcome measure and baseline demographic and clinical characteristics and baseline treatment utilization measures as the independent variables in the

<sup>15 Rosenbaum PR and Rubin DB. The central role of the propensity score in observational studies for causal effects. Biometrika. 70(1):41–55, 1983.

<sup>16 Rosenbaum PR, Rubin DB. Reducing bias in observational studies using subclassification on the propensity score. J Am Stat Assoc 1984; 79:516-24.

<sup>17 Rubin DB. The design versus the analysis of observational studies for causal effects: parallels with the design of randomized trials. Stat Med 2007; 26:20-36.

model. These independent variables will be selected *a priori* based on literature and expert opinion as potential confounds (i.e., factors related to both cohort and outcome). The final list of independent variables to be included in the propensity score model will be determined following review of the baseline descriptive statistics. A 0.10 significance level will be used for independent variables entering and remaining in the model.

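### The one-year cost and utilization models list no baseline cost or encounter term, and the propensity model is not certain to supply that adjustment

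*Protocol*

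**What the plan says.** Table 1 in Section 9.2 collects two sets of pre-index economic variables: "All-cause medical encounters during baseline (n, %, mean, SD, median") and "All-cause costs during baseline (mean, SD, median"). The costs are split into total, medical, inpatient, emergency, outpatient and pharmacy. These are the pre-index counterparts of the one-year all-cause outcomes in Objective 5.

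Section 9.6.5.2, under Resource Utilization, Costs, and Treatment Patterns, gives the regressors of the outcome models. Besides treatment cohort, "propensity score strata, and the cohort-by-propensity score strata interaction term will be included as independent variables". The time-to-event paragraph just before it defers further model details to the SAP; this one does not.

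Section 9.6.4 describes the propensity candidates as "baseline demographic and clinical characteristics and baseline treatment utilization measures as the independent variables in the" model. In Table 1 the treatment utilization row is defined by "Baseline medication use (n", %), while encounters and costs have rows of their own. The candidate list is not closed: "The final list of independent variables to be included in the propensity score model will be determined following review of the baseline descriptive statistics". Those descriptives do cover the economic variables, since Section 9.6.2 states that "Demographic, clinical, and other baseline variables (including resource use and cost) will be summarized by cohort".

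**The concern.** Prior spending generally predicts later spending. Section 7 reports that, in an earlier hospital-database study, prasugrel and clopidogrel patients differed markedly in profile, so their baseline spending may well differ too. If a gap in baseline cost survives the propensity adjustment and the outcome model has no term for it, part of that gap carries into the one-year cost difference and can be read as a drug effect.

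The protocol has two places where this could be prevented, and neither is secured. The outcome model lists no baseline value. The propensity model might include one, but only if it is added to the candidate list and then passes a test that looks at treatment assignment alone. Section 12 plans an abstract on the economic endpoints and considers a separate manuscript, so the economic contrast will be read in its own right.

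**Working it through.** **The plan's own figure.** No SD, sample size or power is given for costs or utilization. The only power statement is for MACE: 92% in Section 9.4. It reproduces with 5,101 prasugrel and 3 × 5,101 = 15,303 clopidogrel patients.
- Prasugrel risk = 1 − (1 − 0.12)^0.85 = 0.103.
- Events ≈ 15,303 × 0.12 + 5,101 × 0.103 ≈ 2,362.
- Power = Φ(√(2,362 × 0.25 × 0.75) × |ln 0.85| − 1.96) = 92.8%. A two-proportion calculation gives 91.6%.

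This does not bear on the cost models. It only confirms the group sizes used below.

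**Where baseline cost could be adjusted for**

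| Place | What the protocol states | Baseline cost or encounters? |
|---|---|---|
| Outcome model (9.6.5.2) | Cohort, strata, interaction | Not listed |
| Propensity candidates (9.6.4) | Demographic, clinical, treatment utilization | Not named, not excluded |
| Propensity entry rule (9.6.4) | Stepwise, p<0.10 for association with treatment | Only if associated with cohort |
| Post-match comparison (9.6.4) | Characteristics in the propensity model | Only if already selected |
| ANCOVA/OLS for costs (9.6.6) | Optional sensitivity analysis | No baseline-cost covariate specified |

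Matching is the primary method and strata belong to the fallback. Read literally under matching, the listed outcome-model terms reduce to cohort alone.

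**Size of a residual bias.** Inputs from the protocol: 5,101 and 15,303 patients, and the 0.10 standardized-difference rule of thumb. Assumed, because the protocol gives no value: the baseline-to-follow-up correlation ρ, the leftover gap d, and a linear normal approximation.
- SE of a mean difference = √(1/5,101 + 1/15,303) = 0.0162 SD.
- Bias = ρ × d (in SD). False-positive rate under no effect = 1 − Φ(1.96 − bias/SE) + Φ(−1.96 − bias/SE).

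| d (SD) | ρ | Bias (SD) | Bias/SE | False-positive rate |
|---|---|---|---|---|
| 0.10 | 0.3 | 0.030 | 1.9 | 46% |
| 0.10 | 0.5 | 0.050 | 3.1 | 87% |
| 0.05 | 0.3 | 0.015 | 0.9 | 15% |
| 0.05 | 0.5 | 0.025 | 1.5 | 34% |

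**Fewer patients.** The 5,101 required 180 days of enrollment after discharge, but Section 9.1.4 assigns costs to the fixed 12-month period. If half remained (an assumption), SE = 0.0162 × √2 = 0.0229 SD. For d = 0.10 the shift is then 0.030/0.0229 = 1.3 SE (about 26%) at ρ = 0.3, and 0.050/0.0229 = 2.2 SE (about 59%) at ρ = 0.5.

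**Precision.** Adjustment multiplies the variance by 1 − ρ². For a difference detectable with 80% power unadjusted (2.80 × 0.0162 = 0.045 SD), power becomes Φ(2.80/√(1 − ρ²) − 1.96): 84% at ρ = 0.3, 86% at 0.4 and 90% at 0.5. The starting difference is already very small, so this gain is modest in practice.

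**The case against.** A reader might infer that baseline cost enters neither model and so is adjusted for nowhere. The protocol does not support that. The final propensity list is decided after descriptives that include resource use and cost. If those variables were selected, matching or stratification would adjust for them. The abstract's list of covariates is also open-ended, and the narrow sense of treatment utilization rests on one row label in Table 1.

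Nor can it be said that an imbalance in baseline cost would certainly go unnoticed. The quality check described under Propensity Score Stratification, which applies to either method, uses standardized differences and is not expressly limited to model variables. Model changes to improve balance are allowed.

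Two further objections have weight. The sentence on strata fits the fallback, so the covariates of the matched economic analysis are not spelled out. And covariates of a secondary model are often left to the SAP. But this paragraph does state a regressor list and does not defer it. The freedom it gives to use alternative models follows an assessment of the outcome's distribution, which concerns model form. The point is thus an improvement to a stated model, not a complaint about missing detail.

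The objection to the size also stands in part. The relevant ρ is the one left after comorbidity, prior MI, prior revascularization and medication use have been balanced, and it may be lower than the marginal value. The planned cost model is gamma with a log link, not linear.

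**Conclusion.** The point holds in a limited form. Baseline costs and encounters are collected, they are absent from the stated cost and utilization models, and they are not named as propensity candidates. Adjustment of the economic comparison for its own baseline value is possible but not assured.

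Residual bias is the main concern. For a 0.10 SD leftover gap and ρ of 0.3 to 0.5 the shift is about 1.9 to 3.1 SE. This rests on an assumed ρ, an assumed gap, a linear scale and the preliminary counts in Section 9.4, and it shrinks if other propensity covariates already explain baseline cost or if fewer patients have a full year. It shows what an unadjusted gap could do; it does not predict that such a gap will occur. Precision is a modest extra. The primary MACE analysis is not touched; only the secondary economic objectives are.

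**What to change.** In Section 9.6.5.2, pre-specify the matching baseline value as a covariate in each one-year cost and utilization model, whether matching or stratification is used. Examples are log(1 + baseline all-cause cost) in the gamma/log-link cost models and the corresponding baseline encounter count in the utilization models.

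In Section 9.6.4, include baseline cost and encounters in the post-adjustment balance table under the existing 0.10 standardized-difference rule, whether or not they enter the propensity model.

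The data are already collected, so the change is a few lines of wording. The price is one extra covariate per model and a choice of functional form for a skewed baseline cost, to be made before any outcome is analysed.

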### 9.6.6. Sensitivity Analyses

The following sensitivity analyses may be performed:

1. To assess the robustness of the results to the potential for unmeasured confounding (confounding variables not captured in the analysis database, such as blood pressure), a sensitivity analysis will be conducted using the rule-out method.

The rule-out method graphically depicts the level of unmeasured confounding necessary to explain the observed treatment difference. The level of unmeasured confounding is quantified by 1) the association between the unmeasured confounder and treatment choice; and 2) the association between the unmeasured confounder and outcome. While the true level of unmeasured confounding remains unknown, if the rule-out method demonstrates that it would require very strong levels of unmeasured confounding to eliminate ('rule out') the observed treatment difference, then the analysis is considered more robust than if only weak levels of unmeasured confounding would rule out the observed result.

2. To assess the robustness of the results to modeling assumptions, method selection, and other statistical assumptions, alternative methods may be used as appropriate. Although Central Limit Theorem (CLT)-based methods are more sensitive to extreme distributions in small samples, the current study sample is large enough to justify their efficiency and reliability in analyzing costs. Therefore, CLT-based methods (ANCOVA or traditional OLS models) may be used as a sensitivity analysis of costs and other continuous dependent variables. Multivariate logistic regression without propensity adjustment may be used as sensitivity analysis for categorical outcome variables. Independent variables will include all independent variables in the final propensity model. Bootstrapping (e.g., for cost and any other skewed outcomes) may be conducted as appropriate.

*Note*: If propensity score matching is used for adjustment in the primary analysis, then sensitivity analyses may include the use of propensity score stratification and the same outcomes model used in the primary analysis. If propensity score stratification is used for adjustment in the primary analysis, then sensitivity might include the use of the same propensity model with a different outcomes model OR a regression model without propensity adjustment.

3. Sensitivity analyses may also be conducted to assess generalizability of the results using the primary methods/models but:

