# 8. Research Objectives

The overall hypothesis of this study is that, after adjustment for baseline differences, prasugrel will be associated with a significantly lower risk of major adverse cardiovascular events (MACE) than clopidogrel up to one year post-discharge from the index hospitalization.

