These counts are for informational purposes only and may not represent the actual number of enrollees available for analysis. Application of other selection criteria required for this study or other factors may further reduce the available sample size. However, for the primary population, ACS-PCI patients with no history of TIA or stroke, treated with prasugrel or clopidogrel post-discharge from the index hospitalization (Table 2), the above sample sizes will provide 92% power at a 0.05 two-sided significance level to detect a 15% reduction in the adjusted hazard ratio (HR=0.85), assuming a clopidogrel base rate of 12% for MACE up to one year after the index hospitalization discharge and a 3:1 clopidogrel to prasugrel ratio. Of note, the study power

will vary as a function of both the clopidogrel event rates (as shown in Figure 2) and the magnitude of the treatment effect.

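### The rule-out analysis is described only against the observed treatment difference, while the primary hypothesis is a significant reduction in MACE, which weaker unmeasured confounding would undo

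*Protocol*

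**What the plan says.** Section 9.6.6, item 1, commits to a rule-out analysis for unmeasured confounding in these terms: "The rule-out method graphically depicts the level of unmeasured confounding necessary to explain the observed treatment difference". It gives the two axes of the plot, the confounder's association with treatment choice and its association with outcome. It then says how the plot will be read. The yardstick is how strong the confounding must be "to eliminate ('rule out') the observed treatment difference". Where the answer is that it must be very strong, the protocol draws this conclusion: "then the analysis is considered more robust than if only weak levels of unmeasured confounding would rule out the observed result". No confidence limit, loss of significance or numerical cut-off is mentioned. The list containing this item opens with "The following sensitivity analyses may be performed", although item 1 itself is worded as a commitment.

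Section 8 states the hypothesis that, after adjustment, "prasugrel will be associated with a significantly lower risk of major adverse cardiovascular events (MACE) than clopidogrel". Section 9.6.5.2 sets the significance level at p<0.05. Section 9.4 gives the design values: "the above sample sizes will provide 92% power at a 0.05 two-sided significance level" for HR 0.85, "assuming a clopidogrel base rate of 12% for MACE up to one year", and a 3:1 clopidogrel-to-prasugrel ratio.

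**The concern.** The natural reading of item 1 is that the plot shows the confounding needed to bring the hazard ratio to 1. The study's primary claim is stronger than an estimate below 1: it is a significant reduction. That claim fails as soon as bias of the relevant size carries the upper 95% limit to 1, when the estimate is still below 1. The planned plot therefore answers an easier question than the one the primary conclusion raises, and the protocol already links the answer to a statement about robustness.

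This matters because section 7 acknowledges that claims analyses may be biased by residual confounding and reports marked baseline differences between prasugrel and clopidogrel patients in an earlier database study. Item 1 is the only quantitative bias analysis in section 9.6.6. The primary estimate and its test are not affected. What is at stake is how securely the primary finding is said to stand.

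**Working it through.** **Inputs from the protocol.** 5,101 prasugrel patients (section 9.4, Table 2). Clopidogrel one-year MACE 12%, HR 0.85, 3:1 ratio, two-sided 0.05, power 92% (section 9.4). Matching anywhere from 1:1 to 1:3 (section 9.6.4). On-treatment censoring in the primary analysis (section 9.6.5.2).

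**Step 1: reproduce the stated power.**
- Clopidogrel patients at 3:1: 3 × 5,101 = 15,303.
- Prasugrel risk under proportional hazards: 1 − 0.88^0.85 = 10.3%.
- Events: 5,101 × 0.103 + 15,303 × 0.12 ≈ 2,362.
- SE(log HR) = 1/√(2,362 × 0.25 × 0.75) = 0.0475.
- z = |ln 0.85|/0.0475 = 0.1625/0.0475 = 3.42.
- Schoenfeld power = Φ(3.42 − 1.96) = 92.8%. A two-proportion calculation gives 91.6%. The stated 92% is reproduced.

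**Step 2: interval at the design values.** exp(ln 0.85 ± 1.96 × 0.0475) = 0.774 to 0.933.

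**Step 3: bias needed.**
- To move the estimate to 1: factor 1/0.85 = 1.18.
- To move the upper limit to 1: factor 1/0.933 = 1.07.
- Ratio on the log-HR scale: z/(z − 1.96) = 3.42/1.46 = 2.34.

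**Step 4: as confounder strength.** The equal-strength association (same RR with treatment and with outcome) is r + √(r(r − 1)), where r is the bias factor. This gives 1.63 for the estimate and 1.35 for the limit.

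**Step 5: a binary confounder.** Its prevalence and strength are assumptions; the protocol gives neither.
- Confounder RR 2, prevalence 30% in clopidogrel. Solve (1 + p)/(1 + 0.30) = target for the prasugrel prevalence p. Estimate: 0.85 × 1.30 − 1 = 10.5%, an imbalance of 19.5 points. Limit: 0.933 × 1.30 − 1 = 21.3%, an imbalance of 8.7 points.
- Confounder–treatment odds ratio 1/2. With 50% prevalence in clopidogrel, the outcome RR needed is 2.64 against 1.50. With 20% prevalence it is 3.55 against 1.89.

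**Step 6: how far the ratio varies.** The 20% and 40% event losses are assumed values for on-treatment censoring.

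| Observed HR and setting | 95% CI | Log-HR ratio | Equal-strength RR: estimate / limit |
|---|---|---|---|
| 0.75, 3:1 | 0.682–0.824 | 1.49 | 2.00 / 1.72 |
| 0.80, 3:1 | 0.728–0.879 | 1.72 | 1.81 / 1.53 |
| 0.85, 3:1 | 0.774–0.933 | 2.34 | 1.63 / 1.35 |
| 0.88, 3:1 | 0.802–0.966 | 3.65 | 1.53 / 1.23 |
| 0.90, 3:1 | 0.820–0.987 | 8.24 | 1.46 / 1.13 |
| 0.85, 2:1 | 0.770–0.939 | 2.57 | 1.63 / 1.33 |
| 0.85, 1:1 | 0.757–0.955 | 3.51 | 1.63 / 1.27 |
| 0.85, 3:1, 20% fewer events | 0.766–0.943 | 2.78 | 1.63 / 1.31 |
| 0.85, 3:1, 40% fewer events | 0.754–0.959 | 3.84 | 1.63 / 1.26 |

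The gap is widest where the result is only just significant.

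**The case against.** The strongest reply is that nothing here is stated wrongly. Losing significance always takes less confounding than removing the effect, for any interval that excludes 1. Asking what would explain away the observed difference is a legitimate question. Item 1 never says that the target is a hazard ratio of exactly 1, its last clause speaks more loosely of the result, and nothing prevents the SAP from adding a curve for the limit. The analysis is supportive, and the list containing it is introduced as optional.

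Much of this stands. The estimate curve should stay, and the SAP may already contain the second one. But the protocol does more than name a method. It states the target twice as the observed difference and says how the answer will be read as robustness. As written, that reading does not address the conclusion in section 8.

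Three stronger readings are tempting, and the document does not support them.
- A reader might infer that a fragile result would be reported as robust. Item 1 sets no cut-off, its wording is comparative, and it reserves the favourable reading for very strong confounding. Nothing shows that an association of 1.63 would be so labelled.
- A reader might infer that the protocol regards unmeasured confounding as its main threat. It ranks no threat first; section 9.8 lists unavailable confounders as one limitation among several.
- A reader might infer that key confounders such as weight are simply missing. Table 1 marks weight as available in claims, while section 9.8 says it is generally not. Sections 8.3 and 9.8 also offer chart review and socioeconomic data as partial remedies, although section 9.4 says the chart subset lacks power for outcome comparisons.

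**Conclusion.** The point holds in a limited form. A robustness statement based only on the observed difference can overstate how secure the significant primary finding is. At the design values the bias needed differs by a factor of about 2.3 on the log-HR scale, or RR 1.63 against 1.35 as equal-strength associations.

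It would be tempting to say that robustness is overstated by about a factor of two. The document does not support that as a general figure. The ratio depends on the observed HR, the number of events, the matching ratio and the scale. On the log-HR scale it lies between about 1.5 and about 8 in the scenarios tried. Measured as excess equal-strength RR at the design values it is 0.63/0.35 = 1.8.

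The illustration assumes the section 9.4 sample sizes, a 3:1 match of all prasugrel patients, full-year event rates without on-treatment censoring, and an approximate standard error that ignores any correlation from matching. The direction of the conclusion depends on none of these. This affects the interpretation of a supportive analysis, not the primary estimate.

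**What to change.** In section 9.6.6, item 1, specify that the rule-out curve will be drawn for the 95% confidence limit nearest 1 as well as for the point estimate. State that any claim that the significant MACE finding is robust to unmeasured confounding will rest on the confidence-limit curve, with the estimate curve kept to show what would explain the whole observed difference. If the SAP already provides this, aligning the protocol wording is enough.

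The cost is one more curve on the same plot, with no new data. The reported robustness will look less favourable, most of all if the result is only just significant.
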